## 10.0 Privacy/Confidentiality Issues

Covariates	df
Vitamin D vs placebo	1
Age	2
Severity of illness (SOFA)	2
Comorbidity (Charlson)	2
Pre-existing cognitive impairment	1
Time to long-term cognitive assessment	2
Premorbid intelligence	1
ARDS development	1

**Table 2.** Covariates for the multivariable linear regression models.

[name], MSc  
VIOLET-BUD

The patient's information, without identifiers, may be shared with other institutions or universities. [name], his co-investigators, and their staff will comply with any and all laws regarding the privacy of such information. There are no plans to pay the patient for the use or transfer of their de-identified information or specimens.

## 11.0 Follow-up and Record Retention

The duration of this study is approximately one year. We will try to enroll 140 patients during this time. Data collected will be retained indefinitely.

## 2. Introduction

This is the Statistical Analysis Plan (SAP) for the study titled, “Vitamin D to Improve Outcomes by Leveraging Early Treatment: Long-term Brain Outcomes in Vitamin D Deficient Patient of Acute Lung Injury (PETAL) randomized control trial titled, “Vitamin D to Improve Outcomes by Leveraging Early Treatment” (VIOLET, [NCT03096314](#)) which was published in the *New England Journal of Medicine*. VIOLET-BUD was sponsored by the NHLBI (R56HL141567).

### 2.1. Background and rationale

One out of four intensive care unit (ICU) survivors will develop long-term cognitive impairment (LTCI) similar in severity to mild Alzheimer’s disease. A substantial proportion will also develop impairments in executive function, which leads to increased disability, worsening quality of life, and reduced employment. Interventions that preserve long-term cognition and executive function after critical illness are lacking.

Early, high-dose oral Vitamin D repletion could potentially help preserve long-term cognition in critically ill patients. Vitamin D is a pleiotropic secosteroid hormone that modulates systemic and central nervous system (CNS) inflammatory responses. Inflammation in response to an acute illness plays a prominent role in dementia pathogenesis. An abundance of recent observational data suggest Vitamin D deficiency is associated with poorer long-term cognition and increased risk of Alzheimer’s dementia in community-dwelling adults. Vitamin D deficiency is also associated with accelerated cognitive decline in hospitalized, acutely ill patients. To our knowledge, no studies have evaluated if Vitamin D repletion improves these cognitive outcomes in the setting of an acute or critical illness.

### 2.2. Objectives

VIOLET-BUD is an ancillary study to the parent VIOLET study. Its primary objective and hypothesis are:

To determine if early administration of a single high-dose (540,000 IU) oral vitamin D3 (cholecalciferol) treatment improves long-term global cognition and executive function as determined by comprehensive neuropsychological testing in critically ill patients with Vitamin D deficiency at enrollment. *We hypothesize that critically ill patients with Vitamin D deficiency who are treated with a single high-dose of Vitamin D3 will have significantly better long-term global cognition and executive function than those treated with placebo.*

### 3. Study Population

VIOLET-BUD enrolled subjects from November 2018 to October 2019 in 7 (out of 42) PETAL sites that participated in VIOLET. The local site contacted all patients who were enrolled in VIOLET to recruit patients for VIOLET-BUD. Originally, the objective was to conduct the follow-up assessments 12  $\pm$  4 months after randomization. Due to slower than anticipated enrollment, VIOLET-BUD expanded the follow-up window from 12 months to include all survivors. The median (interquartile range) time from randomization to follow-up was 443 (386.5, 481.5) days.

Patients were excluded from VIOLET-BUD if they were deaf, blind, or non-English speaking. Patients who were deaf or blind were excluded, because the neuropsychological testing has auditory and visual components. Non-English speaking patients were excluded because the neuropsychological raters can only perform the assessments in English.

### 4. Variables Collected for VIOLET-BUD

#### 4.1 Primary Outcome Variables

The primary outcomes for VIOLET-BUD are long-term global cognition and executive function, as determined by a comprehensive neuropsychological assessment. Global cognition was assessed for using the ***Repeatable Battery for the Assessment of Neuropsychological Status (RBANS)***. The RBANS is a comprehensive neuropsychological battery for the evaluation of global cognition and has been validated in subjects with mild cognitive impairment, moderate to severe traumatic brain injuries, vascular dementias, and Alzheimer's disease. In addition to providing a score for global cognition, it also provides individual scores for immediate and delayed memory, attention, visuospatial construction, and language.

To quantify executive function, we used tests from the ***Delis–Kaplan Executive Function System (D-KEFS)***. An executive function composite score was calculated using scores from the ***DKEFS Proverbs, Trail Making-Number/Letter Switching, and Verbal Fluency Category Switching subscales***.

#### 4.2. Secondary Outcomes are listed in Table 1.

Study Assessment	Description
RBANS cognitive domains	Immediate memory, delayed memory, attention, visuospatial construction, and language
Katz Activities of Daily Living (ADL) 	Quantifies basic ADLs such as bathing, dressing, toileting, transferring, continence, and feeding.
Lawton Instrumental Activities of Daily Living Scale (IADL) 	Quantifies the patient's IADLs, such as his/her ability to use the telephone, shopping, food preparation, housekeeping, laundry, transportation, medication management, and finances.

Table 1. Secondary outcomes for VIOLET-BUD.

#### 4.3. Additional Variables

The patient was considered to have ***pre-existing cognitive impairment*** if he/she had a past history of dementia or was on an acetylcholinesterase inhibitor medication (galantamine [Reminyl], Donepezil [Aricept] and rivastigmine [Exelon]) prior to randomization. ***Pre-illness intelligence*** was estimated using the Barona Index, which is based upon age, region of residence, education, and highest occupation. ***Severity of illness*** at enrollment was characterized using the Sequential Organ Failure Assessment. ***Infection*** at enrollment was defined by the presence of sepsis or pneumonia.

## 5. Statistical Methods

All long-term outcomes will be analyzed using both univariate methods and multivariable regression, adjusting for covariates noted below. Though baseline patient characteristics should theoretically be balanced between treatment groups due to randomization, adjustment increases our power and precision. Adjusted analyses will be considered the primary analyses.

### 5.1. Unadjusted analyses

We will analyze normally distributed outcomes using the t-test and non-normally distributed outcomes using the Mann-Whitney test.

### 5.2. Adjusted analyses

$$\begin{array}{l} \text{Long-term RBANS} = \boxed{\text{Vitamin D versus Placebo}} + \text{Covariates} \\ \\ \text{Long-term executive function} = \boxed{\text{Vitamin D versus Placebo}} + \text{Covariates} \\ \text{composite score} \end{array}$$

**Figure 1.** Multivariable linear regression models

Covariates	Variable Type	df	Comment
Vitamin D vs placebo	Dichotomous	1	Primary independent variable
Age at enrollment	Continuous	2	
Pre-existing cognitive impairment	Dichotomous	1	Dementia or use of cholinesterase inhibitor prior to randomization
Severity of illness at enrollment	Continuous	2	Sequential Organ Failure Assessment (SOFA) score prior to randomization
Infection (Sepsis + Pneumonia) at enrollment	Dichotomous	1	Obtained by medical record review
Pre-illness intelligence at enrollment	Continuous	2	The Barona Index which is based on level of education, highest occupation, and region of residence 

**Table 2.** Covariates for the multivariable linear regression models in order of importance. The models will be able to accommodate 9 degrees of freedom.

To determine if single, high-dose enteral Vitamin D treatment improves long-term global cognition and executive function compared with placebo, we will use multivariable linear regression or proportional odds logistic regression models based on the distribution of the continuous outcomes (**Figure 1**). Separate models will be constructed for long-term RBANS and executive function and adjusted for the baseline covariates listed in **Table 2**. Post-randomization covariates (e.g., interventions provided during hospitalization) will not be adjusted for because they may potentially be affected by the randomized intervention and be on the causal pathway. Prior to modeling, we will perform redundancy analyses to ensure that no covariates completely explain any of the others (resulting in multicollinearity) using an adjusted  $R^2$  cutoff of 0.7. If any covariates are highly correlated, only one of them based on clinical relevance will be kept in the model. If the multivariable models do not converge due to limited variability or low number of patients in specific levels of certain covariates, the number of covariates will be reduced based on the least rank in the order specified above. Restricted cubic splines for continuous variables will be incorporated into the models based on the distribution. To account for correlation among patients within a given site, we will adjust standard errors using Huber-White sandwich estimate. Partially missing long-term outcomes will be imputed using single imputation.

As exploratory heterogeneity of treatment effect analyses for primary outcomes, we will evaluate for effect modification by age, pre-existing cognitive impairment (e.g., dementia), baseline severity of illness (Sequential Organ Failure Assessment), infection (pneumonia or sepsis diagnosis), and pre-morbid intelligence (Barona). Because this is an exploratory analysis, we will consider an interaction term p-value less than 0.20 to suggest the potential presence of effect modification.

To determine how time to neuropsychological assessment impacted our findings, we will also conduct a sensitivity analysis; we will re-run the multivariable regression models adjusting for time to neuropsychological assessment. Patients were included in VIOLET (and VIOLET-BUD) if their plasma Vitamin D concentrations were < 20 mg/dL as determined by local immunoassay (clinical laboratory or point-of-care) testing. The VIOLET parent trial also confirmed baseline (pre-randomization) Vitamin D deficiency using liquid chromatography-mass spectrometry (LC-MS), the gold standard for Vitamin D measurement, conducted at the University of Washington on batched samples after 90-day follow-up was completed. VIOLET-BUD's primary analyses will use immunoassay Vitamin D measurements. We will re-run the multivariable regression models and adjust for baseline Vitamin D levels as measured by LC-MS as a sensitivity analysis. Because the VIOLET parent study did not observe a significant difference in 90-day mortality between the Vitamin D and placebo groups, analyses accounting for differential mortality will not be performed.

Other secondary analyses will include associations between Vitamin D treatment and individual RBANS cognitive domains (e.g., immediate and delayed memory, attention, visuospatial construction, and language) and executive function subscales (DKEFS Proverbs, Trail Making-Number/Letter Switching, and Verbal Fluency Category Switching). We will also determine if treatment is associated with functional status (Katz and Lawton).

Level of statistical significance will be set at 5%. All tests will be two-sided and 95% confidence intervals will be reported along with all effect estimates. Presentation of results will emphasize clinical significance, effect sizes, and confidence intervals, over statistical significance. Regarding the analyses of all *a priori*-defined secondary outcomes described herein, no adjustments will be made for multiple comparisons in keeping with recommendations on this topic and standard practice when analyzing multiple, prospectively defined outcomes in a clinical trial.

The Outcomes After Critical Illness and Surgery (OACIS) Employment Status Questionnaire and place of residence were originally intended to be secondary outcomes. Due to the categorical nature of and low number of patients with these outcomes (loss of employment or nursing home), their statistical analyses will be descriptive in nature. Death was also a secondary outcome but will be analyzed as a separate manuscript.

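### The SAP's non-convergence rule drops covariates by importance rank rather than by cause, so it can discard sound adjustment before reaching the covariate that failed

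*SAP*

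**What the plan says.** SAP section 5.2 sets the fallback for models that "do not converge due to limited variability or low number of patients in specific levels of certain covariates". In that case, "the number of covariates will be reduced based on the least rank in the order specified above". The order is that of SAP Table 2, whose caption reads "Covariates for the multivariable linear regression models in order of importance". From the top, the rows are:

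- treatment (1 df)
- age (2 df)
- pre-existing cognitive impairment (1 df), defined as "Dementia or use of cholinesterase inhibitor prior to randomization"
- SOFA (2 df)
- "Infection (Sepsis + Pneumonia) at enrollment" (1 df)
- "Pre-illness intelligence at enrollment", measured by the Barona Index (2 df)

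The same section permits "multivariable linear regression or proportional odds logistic regression models based on the distribution of the continuous outcomes". SAP section 5 makes the adjusted analyses primary and gives gains in power and precision as the reason for adjusting. Nothing in either document says that the covariate causing a failure is to be removed, combined or penalised.

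**The concern.** The trigger and the remedy do not match. The trigger is a fault in particular covariates, but the remedy works up from the bottom of a list ordered by importance. An importance ranking suits a shortage of degrees of freedom. It does not suit a fault that sits in one column.

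The two adjustment covariates with levels that can be sparse are the dichotomous ones, pre-existing cognitive impairment and infection. Neither is last. Followed literally, the rule first removes a continuous covariate that may be sound, and the model still cannot be fitted. What is at stake is the precision that adjustment was meant to buy, in a study that enrolled 95 patients against a planned 140.

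**Working it through.** **Inputs from the documents.** N = 95, RBANS SD 12.4, two-sided alpha 0.05 and a detectable difference of 7.2 points at more than 80% power (SAP, Sample Size Calculations); 1:1 allocation (protocol section 4.0); ranking and df (SAP Table 2).

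**The SAP's own figures.** With 47.5 patients per arm, SE = 12.4 × √(2/47.5) = 2.544. Power = Φ(7.2/2.544 − 1.96) = Φ(0.870) = 80.8%. With the noncentral t and arms of 47 and 48 it is 79.96%. The SAP's statement is reproduced to within rounding. The df budget also agrees: 1+2+1+2+1+2 = 9, and 95/10 = 9.5.

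**Removal path.** Leaving out treatment, 8 adjustment df remain.

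- Impairment at fault: Barona (2), infection (1) and SOFA (2) go first, 5 of 8 df. Removing the cause alone costs 1 df.
- Infection at fault: Barona goes first, 2 of 8 df. Removing the cause alone costs 1 df.

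**Linear model.** The design matrix has an intercept plus 9 columns. Suppose no patient has pre-existing impairment, so that the column is constant:

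| Covariates removed | Columns | Rank |
|---|---|---|
| none | 10 | 9 |
| Barona | 8 | 7 |
| Barona, infection | 7 | 6 |
| Barona, infection, SOFA | 5 | 4 |
| impairment only | 9 | 9 |

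Every step of the ranked rule leaves the matrix one short. Removing the cause restores full rank at once. With 1 or 3 impaired patients the full matrix has rank 10 of 10, so mere sparsity does not stop a linear fit.

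**Proportional odds model.** If the impaired patients hold the lowest (or the highest) scores in the data, the likelihood keeps rising as the impairment coefficient goes to infinity. That is true of any model that contains the column, so removing other covariates cannot help. In simulations with N = 95 and 1 to 3 impaired patients, under assumed outcome models:

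- RBANS-like outcome: 45 of 900 data sets were separated. All 45 stayed so after Barona, infection and SOFA were removed; none did after impairment alone was removed.
- Outcome with a ceiling, like Katz: 342 of 900 were separated. 318 stayed so after Barona was removed, against 37 after impairment alone was removed.

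**How likely is a constant column?** The documents give no prevalence of pre-existing impairment. For assumed values of 1%, 2%, 3% and 5%, the chance of no impaired patient among 95 is (1−p)^95 = 38%, 15%, 6% and 1%.

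**Cost of losing Barona alone.** Its partial R-squared (R²) is not in the documents, so a range is assumed. Residual variance rises by 1/(1−R²). Power is for 7.2 points in a linear model. Reading A takes 12.4 as the residual SD without Barona; reading B takes it as the residual SD with Barona.

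| Partial R² | Variance factor | A: kept → dropped | B: kept → dropped |
|---|---|---|---|
| 0.05 | 1.05 | 82.7% → 80.8% | 80.8% → 78.8% |
| 0.10 | 1.11 | 84.7% → 80.8% | 80.8% → 76.6% |
| 0.20 | 1.25 | 88.6% → 80.8% | 80.8% → 71.6% |
| 0.30 | 1.43 | 92.3% → 80.8% | 80.8% → 65.8% |

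The information lost equals 95 × R², or about 5, 10, 19 and 29 patients.

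**The case against.** The strongest reply is that the rule will probably never act on the primary models. SAP Figure 1 and the Table 2 caption describe linear regression, which has a closed form and fits with a sparse binary covariate. Even under proportional odds, with 1 to 3 impaired patients assumed, 45/900 = 5% of the RBANS-like data sets failed. The rule is also fixed in advance, leaves no discretion and touches only baseline covariates. All of this stands. It limits how far the point reaches, but it does not make the rule suit its purpose.

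Four stronger readings are tempting, and the documents do not support them.

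- *The planned treatment-by-impairment interaction makes failure of the primary analysis likely.* That interaction is exploratory. The fallback sentence comes before it and speaks of covariates. If all impaired patients fell in one arm, the main-effects linear model would still fit and would lose nothing.
- *The cause is never removed.* Repeated application does reach it, after 2 or 5 df have been discarded.
- *Barona can never be the cause.* The trigger includes limited variability as well as sparse levels. A heavily tied continuous score could give a degenerate spline term.
- *A definite loss of power follows.* SAP section 4.3 lists age among the inputs to the Barona Index, and age stays in the model. What Barona adds beyond age is unknown.

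A targeted rule is not a complete cure either, as the 37 of 342 Katz-like data sets show. It also needs a fixed order of steps, or it would replace a deterministic rule with a choice made after seeing which fit failed.

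**Conclusion.** The point holds as a minor defect in a contingency rule. Read literally, the SAP discards 5 of 8 adjustment df before reaching pre-existing impairment, or 2 df before reaching infection. When a constant or separating impairment column is the fault, none of the earlier removals resolves it. Those results follow from Table 2 and the structure of the models and need no assumed effect size.

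The primary analysis is exposed only if a covariate is constant or the proportional odds option is used. The consequence is avoidable loss of precision; no bias or inflation of type I error is shown. The size of the loss cannot be derived from the documents: the partial R-squared, the prevalence of impairment and the simulated outcome models are all assumptions.

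**What to change.** Replace the fallback sentence in SAP section 5.2 with:

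*If a model cannot be fitted because of limited variability or sparse levels in an identifiable covariate, that covariate (for a continuous covariate, first its nonlinear term) is removed and all other Table 2 covariates are kept; this is decided without reference to the treatment estimate. The Table 2 ranking is used only when the cause cannot be isolated to one covariate.*

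This gives one action for each type of covariate and keeps the ranking as the fallback for failures that cannot be traced to one term. The cost is one sentence. The downside is that a covariate ranked as more important may be removed while a lower-ranked one stays, but the one removed is a covariate that the data cannot support. Because enrolment is complete, a count of the two dichotomous covariates, pooled over arms, would show before modelling whether the contingency is live.

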## D5.2. Sample Size Calculations

In our original sample size calculations, we used half a standard deviation (SD) of that particular test to define the minimum clinically important difference (MCID) threshold. The SD for the RBANS in our population from previous studies was 12.4. Thus, we considered a 6-point difference to be the MCID threshold for the RBANS. Based upon a two-sided alpha of 0.05 and 80% power, we computed that we would need outcome data in a total of 140 patients with completed follow-up data (~70 patients in each group) to detect a 6-point difference in RBANS between treatment groups. However, VIOLET-BUD enrolled 95 patients; because the VIOLET parent trial stopped enrollment early, no additional patients could be recruited for this ancillary study. However, this sample size still provides us with more than 80% power to detect at least a

7.2-point difference. Some have considered an RBANS difference of 8 points to be the MCID threshold. For our executive function composite score, the SD in our previous population was 2.34. With 95 patients assessed, we will have greater than 80% power to detect a 1.4-point difference in the executive function composite score assuming a two-sided alpha of 0.05.

For our multiple linear regression models, we will have one degree of freedom available for every 10 to 15 patients with completed outcome measurements. Consequently, we will be able to accommodate 9 degrees of freedom for our multivariable models without overfitting.

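### SAP 5.2 rests the primary tests and 95% CIs on a sandwich estimator over 7 sites with no few-cluster correction; clustered by site and applied plain, the nominal 5% test errs about 12–18% of the time in the linear model

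*SAP*

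**What the plan says.** SAP 5 settles which analysis counts: "Adjusted analyses will be considered the primary analyses". SAP 5.2 then gives the rule for their standard errors: "To account for correlation among patients within a given site, we will adjust standard errors using Huber-White sandwich estimate". The supporting citation, SAP reference 30, is by its title about heteroskedasticity rather than clustering. Protocol 9.0 is no more specific: it calls for robust standard errors to handle correlation within a center.

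SAP 3 says that patients were enrolled "in 7 (out of 42) PETAL sites that participated in VIOLET", and the sample size section counts 95 of them. SAP Table 2 spends all 9 model degrees of freedom. SAP 5.2 sets two-sided tests at the 5% level, and "95% confidence intervals will be reported along with all effect estimates". It also says that effect sizes and intervals will be emphasised over significance.

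Neither document says whether the sandwich is clustered by site, which small-sample correction applies, or whether the critical value comes from a normal distribution, a t on residual df, or a t on few-cluster df.

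**The concern.** A site-clustered sandwich estimates the variance of the treatment coefficient from one contribution per site. With many sites this works well. With 7, the estimate is both too small on average and very noisy, so a critical value near 1.96 is too low. Rejections become too frequent and intervals too short. This happens even when there is no within-site correlation, because the problem lies in the number of clusters.

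At stake are the p-value and the CI for both primary outcomes, RBANS and the executive function composite. Since the SAP puts intervals ahead of significance, intervals that under-cover would damage the result that it values most.

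**Working it through.** **Inputs from the documents.** 7 sites (SAP 3); 95 patients and RBANS SD 12.4 (SAP sample size section); 9 model df plus an intercept, so 95 − 10 = 85 residual df (SAP Table 2); two-sided 5% (SAP 5.2); 1:1 allocation stratified by enrolling hospital (Protocol 4.0), so treatment varies within site. Protocol 9.0 mentions six sites in one place; I use 7, and fewer clusters would not help.

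**The plan's own power figure.** Unadjusted two-group comparison, 47 against 48:

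- SE = 12.4 × √(1/47 + 1/48) = 12.4 × 0.2052 = 2.545.
- 7.2 / 2.545 = 2.83, so power ≈ Φ(2.83 − 1.96) = 80.8% (normal), or 80.0% (noncentral t).
- For the composite: 1.4 / (2.34 × 0.2052) = 2.92, giving 83.0% (normal) or 82.3% (t).

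Both figures reproduce, as unadjusted comparisons that do not involve the sandwich.

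**The estimator.** With X_g and e_g the design rows and residuals of site g, the plain clustered form (CR0) is V = (X′X)⁻¹ [Σ_g X_g′ e_g e_g′ X_g] (X′X)⁻¹, with seven terms in the middle sum. CR1 multiplies V by (7/6) × (94/85) = 1.29. CR2 adjusts each site's residuals and is paired with Satterthwaite df. The unclustered forms (HC0, and HC1 with its df correction) sum over patients instead.

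**Simulation under the null, linear model.** N = 95, 7 sites, Table 2's 9 df with 3-knot splines for age, SOFA and the Barona index. The documents give no site sizes, ICC or covariate distributions, so these are assumed:

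- Run A: 3,000 trials per setting; sites equal, 22/18/15/13/11/9/7 or 30/22/15/12/8/5/3; ICC 0, 0.05, 0.10; allocation balanced within site or independent.
- Run B: 6,000 trials per setting; sites 13–14 each, 25/20/16/12/10/7/5 or 40/20/12/9/6/5/3; ICC 0, 0.02, 0.05, 0.10.

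The table gives the range over these runs and smaller checks on similar splits. Monte Carlo SE is at most about 0.4 points near 5% and 0.7 near 15%.

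| Standard error and reference | True error at nominal 5% |
|---|---|
| Site-clustered CR0, normal or t(85) | 12.0–17.8% |
| Site-clustered CR1, normal or t(85) | 8.6–13.7% |
| Site-clustered CR1, t(6) | 4.5–8.2% |
| Site-clustered CR2, Satterthwaite df | 2.9–5.4% |
| Unclustered HC0 | 5.6–7.3% |
| Unclustered HC1 | 3.6–5.6% |
| Model-based, no site term | 3.8–5.6% |
| Model-based, site fixed effects | 4.3–5.6% |
| Model-based, random site intercept, Satterthwaite df (run A only) | 4.5–5.9% |

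Coverage of the plain clustered 95% CI is one minus its error: 100 − 12 = 88% down to 100 − 18 = 82%.

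**What drives it.** In run B, CR0 gave 12.5–14.2% with equal sites, 14.1–15.9% with moderately unequal sites and 16.7–17.8% with very unequal sites. Within each split, moving the ICC from 0 to 0.10 changed little. Equal sites with ICC 0 still gave about 14%. A more lopsided split (50/20/10/6/4/3/2) took CR1 with t(6) to about 10% and CR2 down to 2.1–2.4%.

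**Power of the corrected tests (run A).** If covariates explain nothing, CR1 with t(6) has 80% power at 8.32–9.14 RBANS points. With covariate R² = 0.3 (assumed), multiply by √0.7 = 0.837: 7.0–7.6. The same step gives 7.2–8.5 for CR2, 6.0–6.4 for a random intercept and 6.0–6.7 for fixed effects.

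**The case against.** The strongest reply is that the SAP does not commit itself to the bad version. Read by its citation, the sandwich is a heteroskedasticity-consistent estimator, and with its ordinary df correction that holds the level (3.6–5.6%). An analyst might equally apply a few-cluster correction as a matter of course. This stands in part. A reader might infer that the trial's primary tests will run at 12–18% error, and the documents do not support that, because the variant is left open. But the unclustered reading leaves the sentence's declared purpose unserved, and the clustered reading that does serve it fails unless corrected.

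Second, site sizes and ICC are assumptions. True, but no split tried removes the inflation, and equal sites with ICC 0 already show it.

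Third, treatment is randomised within hospital, so site correlation should barely disturb the treatment comparison. That is right, and it counts against the plain sandwich: model-based errors are close to nominal in the same simulations.

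Fourth, a reader might infer that the claim "this sample size still provides us with more than 80% power to detect at least a" 7.2-point difference is wrong, and likewise "we will have greater than 80% power to detect a 1.4-point difference in the executive function composite score". That is not established. Both are unadjusted figures that reproduce, and at R² = 0.3 even CR1 with t(6) detects 7.0–7.6 RBANS points and, scaling by 2.34/12.4, 1.31–1.44 composite points.

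Finally, SAP 5.2 allows "multivariable linear regression or proportional odds logistic regression models based on the distribution of the continuous outcomes". The figures above cover only the linear model. Figures for proportional odds are unconfirmed, and none is relied on here.

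**Conclusion.** The point holds, conditionally. Followed for its stated purpose and applied plain, the SAP 5.2 rule misses its own 5% level in the linear model: about 12–18% error with a normal or residual-df reference, about 9–14% with CR1 and the same references, and 82–88% coverage for nominal 95% intervals in the plain case. Under the unclustered reading the error is about 4–7%, and within-site correlation is not handled. So one sentence admits tests whose error differs more than threefold, and the reading closest to its purpose is among the worst.

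This rests on 7 sites, 95 patients, 9 model df, and assumed site splits no more uneven than 40/20/12/9/6/5/3; the ICC (0 to 0.10) has little influence. It should be fixed before the primary models are run.

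**What to change.** Replace the sandwich sentence in SAP 5.2 so that neither primary linear model uses an uncorrected 7-cluster sandwich.

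- **Preferred.** Include enrolling site, reflecting the hospital-stratified randomisation, as a random intercept with model-based standard errors and Satterthwaite df, or as fixed effects. The cost is one variance parameter, or about 6 df on top of the 9 that the SAP allows (15 for 95 patients), and more if a site contains several hospitals.
- **Alternative.** Keep the sandwich, but state that it is clustered by site with CR2 and Satterthwaite df for both p-value and CI. This adds no model terms and gives about 3–5% error, but it is conservative and loses power when sites are very uneven.
- **Not as a level-holding option.** CR1 with t on 6 df, which reaches about 8% with uneven sites.

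If a proportional odds model is chosen, the uncorrected site-clustered sandwich should be avoided there too, and the SAP should say what replaces it. Bring reference 30 into line with whichever estimator is named, and reconcile six against 7 sites.

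The 7.2 and 1.4 points need not be restated unless the chosen test, at a stated covariate R², does not deliver them. No new data are needed. Enrolment is over, so the choice can be checked by simulation on the actual site sizes without using outcomes.
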